### 11.2 Justification for Cases

The null hypothesis: the Successful localization probability of the novel localization device isn't higher compared with hookwire.

The alternative hypothesis: the Successful localization probability of the novel localization is higher compared with hookwire.

 $\alpha$  refers to type I error, while  $\beta$  refers to type II error. Here we consider  $\alpha$  as 0.05, and power(1- $\beta$ ) as 80%. According to some reference and our previous study, we consider the Successful localization probability of hookwire as 89% and the Successful localization probability of the novel localization device as 97%, with

one side and the ratio of 2 between control group and intervention group.

We use PASS 11 with Fisher's exact test to calculate the sample size, getting control group with 116 and intervention group with 232. Taking possible 15% drop-out into account, every group will be enrolled 136 patients in the control group and 273 in the intervention group at least. Here, if we can enroll more patients during enrollment time, the patients could be included in our study. This clinical trial can be deemed as successful if the successful localization probability of the novel localization and hookwire is different, addition the successful localization probability of the novel localization has statistic significantly higher than the successful localization probability of hookwire (p < 0.05).

#### 11.3 Statistical Analysis Method

# 11.3.1 General principles

The quantitative data of normal distribution was expressed by average and 95% confidence interval, while the quantitative data of abnormal distribution was expressed by median and interquartile range. Categorical variables were described as numbers and percentages. The two-sided Student's t-test (standard normal distribution) or Wilcoxon rank-sum test (non-standard normal distribution) for continuous variables was used to test differences, and Chi-square test or Fisher's exact test (if expected frequency < 5) were applied for categorical variables. The P-value less than 0.05 was considered a statistical difference. All statistical analyses were using SPSS 22 software (IBM Corporation, Chicago, USA).

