#### • Secondary endpoints

- (1) The probability of pneumothorax, hemorrhage, the pleural reaction of the novel localization device and hookwire;
- (2) The pain degree caused by the novel localization device and hookwire, measured by the visual analog scale (VAS);
- (3) The time required for the localization procedure of the novel localization device and hookwire.

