# 11.4 Significance Level and Power of the Trial

Significance level: 0.05; power: 0.8.

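### With 2:1 arms, the Student's t-test named for continuous variables would miss its 5% level for pain or localization time if the SDs differ between devices and the t-test branch is used

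*Protocol*

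**What the plan says.** Two secondary endpoints in protocol section 7.1 are continuous or treated as such: "The pain degree caused by the novel localization device and hookwire, measured by the visual analog scale (VAS") and "The time required for the localization procedure of the novel localization device and hookwire". The only tests named for them are in the general rule of section 11.3.1: "t-test (standard normal distribution) or Wilcoxon rank-sum test (non-standard normal distribution) for continuous variables". That rule is two-sided, and the same section sets the threshold: "The P-value less than 0.05 was considered a statistical difference". Section 11.4 repeats the 0.05 level.

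The same paragraph switches the summary statistic with the shape of the data: mean and 95% confidence interval if normal, median and interquartile range if not. It gives no criterion for normality, assigns neither endpoint to a branch, and has no rule for unequal variances.

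Section 11.2 describes the allocation as "one side and the ratio of 2 between control group and intervention group" and reports "getting control group with 116 and intervention group with 232". The larger arm is therefore the novel device. After the 15% drop-out allowance, enrolment is at least 136 and 273.

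**The concern.** Student's t-test pools the two sample variances, and the larger arm dominates the pool. If the smaller hookwire arm is the more variable, the pooled standard error is too small and false positives exceed 5%. If the novel-device arm is the more variable, the standard error is too large, so the test is conservative and loses power. With equal arms the two errors cancel almost exactly, so it is the 2:1 allocation that exposes the trial. Two devices with different release mechanisms may well differ in the spread of procedure time, although the documents do not say so.

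At stake is whether the p-values for pain and time carry the stated 5% level. Because the test and the summary both depend on the shape of the data, with no criterion, the analysis of each endpoint would also be settled only after the data are seen, in an open-label trial.

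**Working it through.** **Inputs.** Test and 0.05 two-sided level: section 11.3.1. Arm sizes 116/232 and 136/273: section 11.2. The SDs of pain and time are not given, so the hookwire/novel SD ratio R is assumed to lie between 0.5 and 2, with the novel-device SD set to 1.

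**The plan's own figures.** Drop-out: 116/0.85 = 136.5 (stated as 136) and 232/0.85 = 272.9 (stated as 273), which agree within rounding. For 89% against 97%, exact Fisher power at 116/232 is 84.4% one-sided and 81.3% two-sided. The smallest 2:1 design reaching 80% is 103/206 one-sided and 113/226 two-sided, so the stated numbers are close to the two-sided exact result and somewhat above the one-sided one. The present point does not depend on this, because it needs only the 2:1 arms.

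**Error of the pooled test.** With n1 hookwire and n2 novel-device patients:

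- pooled variance: sp² = [(n1−1)R² + (n2−1)] / (n1+n2−2)
- squared standard error the test uses: P = sp²(1/n1 + 1/n2)
- true squared standard error: T = R²/n1 + 1/n2
- actual two-sided error ≈ 2[1 − Φ(t × √(P/T))], where t is the critical value on n1+n2−2 degrees of freedom

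At 136/273, t = 1.966 on 407 degrees of freedom.

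- R = 2: sp² = (135×4 + 272)/407 = 1.995; P = 0.02198; T = 4/136 + 1/273 = 0.03307; √(P/T) = 0.815; effective cut-off 1.966 × 0.815 = 1.60; error 10.9%.
- R = 0.5: sp² = (135×0.25 + 272)/407 = 0.751; P = 0.00828; T = 0.25/136 + 1/273 = 0.00550; √(P/T) = 1.227; effective cut-off 2.41; error 1.6%.

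Simulation with 100,000 replicates (normal data, equal means) agrees with the closed form:

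| R (hookwire/novel SD) | Pooled, 136/273, closed form | Pooled, 136/273, simulated | Pooled, 116/232, simulated | Welch, 136/273, simulated |
|---|---|---|---|---|
| 0.5 | 1.6% | 1.6% | 1.6% | 5.0% |
| 0.67 | 2.5% | 2.6% | 2.6% | 5.0% |
| 0.8 | 3.4% | 3.5% | 3.5% | 5.0% |
| 1 | 4.9% | 5.0% | 5.0% | 5.0% |
| 1.25 | 6.8% | 6.9% | 6.8% | 5.0% |
| 1.5 | 8.4% | 8.6% | 8.5% | 5.1% |
| 2 | 10.9% | 11.0% | 11.0% | 5.1% |

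The two sample sizes give essentially the same errors, so the problem comes from the allocation ratio and the SD ratio, and more patients do not cure it. With 204/205 patients the pooled test stays between 4.9% and 5.1% over the whole range.

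**The rank-sum branch.** On normal data with equal centres at 136/273 (20,000 replicates), the rank-sum test rejects in 3.6% of trials at R = 0.5, 4.7% at R = 1, 7.0% at R = 1.5 and 8.3% at R = 2. As a test of equal centre it also drifts, though less than the pooled t-test.

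**Both branches together.** If the choice were made by a normality test at the 5% level in each arm (an assumption, since the protocol names no method), about one normal data set in ten would go to rank-sum. In a small simulation the combined rule then rejected in 2.0% of trials at R = 0.5, 5.3% at R = 1 and 10.9% at R = 2, close to the pooled test alone.

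**The case against.** The strongest reply is that the t-test branch may never be reached. Procedure time is usually right-skewed and VAS scores are bounded. With Shapiro–Wilk applied in each arm at 116/232 (again an assumed method), data with skewness 1, or a VAS rounded to whole numbers, were called non-normal in all 1,000 simulated trials, and data with skewness 0.5 in 88%. The rule would then send both endpoints to rank-sum and the pooled figures would not apply. This stands. It makes the point conditional but does not remove it, because the rank-sum branch has its own drift under unequal spread.

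A second reply is that Student's t-test is often a generic label, that SPSS prints the unequal-variance result as well, and that the variant is a detail for the statistical analysis plan. This stands only in part. The section does not use the word pooled, but the test it names is the equal-variance one. Section 11.8 asks for strict adherence to the stated plan and requires ethics committee approval for methods the protocol does not specify. Read literally, reporting the Welch row would need that approval.

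A reader might also infer that the protocol prescribes a formal normality pre-test. It does not: it makes the choice depend on the distribution without saying how that is judged.

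**Conclusion.** The point holds in conditional form and is minor. If the SDs of pain or localization time differ between devices and the t-test branch is used, the named test does not hold its 5% level with these arms. The error is about 1.6% to 11% for assumed SD ratios of 0.5 to 2. It is above 5% when hookwire is the more variable and below 5% when the novel device is. At equal SDs the test is correct.

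A reader might infer that the p-values for these two endpoints will be wrong. The documents do not support that: they give no SDs, and they do not settle which branch will apply. Nor is the trial's main conclusion at risk, because the primary endpoint is binary and section 11.2 defines success on it alone.

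The condition in "The two-sided Student's t-test (standard normal distribution") is also misworded. A VAS score or a time cannot have mean 0 and SD 1; presumably an approximately normal distribution is meant.

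**What to change.** In section 11.3.1, replace Student's t-test and its standard-normal condition with the unequal-variance (Welch) t-test wherever means are compared. Name one analysis per endpoint in advance, with no choice left to the shape of the data. The preferred form for both localization time and VAS pain is the mean difference with a Welch test and 95% confidence interval.

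If a rank-sum test is kept for VAS pain, present it as a comparison of the two distributions and not as a test of equal centre. Moving pain to rank-sum would not by itself cure the unequal-spread problem.

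The cost is a short edit to one section. The loss of power at equal SDs is negligible: at 136/273 the Welch degrees of freedom would be about (1/136 + 1/273)² / [(1/136)²/135 + (1/273)²/272] = 270 instead of 407, which moves the critical value from 1.966 to 1.969. No sample size change is needed, and the software named in the protocol already reports the test.

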#### 6 CLINICAL EVALUATION CRITERIA

# 6.1 Evaluation Criteria of Efficacy

#### • Successful localization rate

Successful localization is defined as: the localization device is released and located in or around the nodule (within 10 mm to the edge of the nodule), and no dislodgement of the device occurred from the localization procedure to the first exploration of VATS. Moreover, no fault or fracture of the device is observed during the whole procedure.

If the localization needle should be changed during the study (for single or multiple nodules), the change information must be recorded. Localization evaluation is performed for all the used products. For multiple nodules (using multiple localization needles), localization is considered as a failure if the localization of one site fails.

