# 11.8 Deviation Reporting Procedures

The original statistical plan should be strictly complied with. Other statistical methods, which are not specified in the protocol, can be used only after having been reviewed and approved by the ethics committee.

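### Localization time is compared with an unstratified two-group test although patients may have one or several nodules; adjusting for the planned number of nodules would recover efficiency at almost no cost.

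*Protocol*

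**What the plan says.** - **Several nodules per patient.** Protocol 6.1 provides for multiple nodules with multiple needles and scores the primary endpoint per patient: "localization is considered as a failure if the localization of one site fails".
- **Time.** Section 7.1 lists as a secondary endpoint "The time required for the localization procedure of the novel localization device and hookwire". It gives no per-nodule scaling and no rule for patients with more than one nodule.
- **Tests.** Section 11.3.1 names a two-sided t-test or Wilcoxon rank-sum test for continuous variables. The same sentence goes on to the categorical ones: "Chi-square test or Fisher's exact test (if expected frequency < 5) were applied for categorical variables". None is stratified or adjusted.
- **Balance.** Section 7.2 describes randomization without strata. Section 7.7 offers propensity score matching if age, gender or lesion location turn out unbalanced. The number of nodules is not on that list.
- **Later changes.** Section 11.8 requires strict compliance with the stated plan and adds: "Other statistical methods, which are not specified in the protocol, can be used only after having been reviewed and approved by the ethics committee".
- **Timing.** Nodules are confirmed by chest CT for inclusion (5.1; Table 1 in 7.5). Envelopes are opened only when the localization procedure begins (7.2).

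**The concern.** A procedure that places two needles should take longer than one that places one. When both kinds are pooled in a two-group test, the difference between one-nodule and multi-nodule patients goes into the error variance, although it is known before allocation and has nothing to do with the device. A real difference in time could be missed for that reason.

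This is more than detail left to a statistical analysis plan. Section 11.3.1 fixes the unstratified test, and 11.8 binds the analyst to it unless the ethics committee agrees otherwise. The one balance safeguard, in 7.7, omits the factor that most plausibly drives procedure length.

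**Working it through.** **The plan's own figures.** The protocol states no sample size, effect or SD for time, so there is no planned power for time to reproduce. The only sizing is for the primary endpoint (11.2): 89% versus 97%, one-sided 0.05, 80% power, "getting control group with 116 and intervention group with 232". Fisher's exact test at 116/232 has 84.4% power one-sided and 81.3% two-sided, so the primary is not undersized at those numbers.

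**Model for time (all inputs are assumptions).** Set the mean single-nodule time to 1. Let q be the share of patients with two nodules, c the coefficient of variation (CV) of a single-nodule time, and f the extra time for a second nodule (1 = a full procedure time, 0.5 = half).

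- Between-stratum variance: q(1−q)f²
- Within-stratum variance: c²(1+qf²)
- R² = between / (between + within)
- If the stratified comparison has 80% power at two-sided 0.05, unstratified power = Φ[(1.960+0.842)·√(1−R²) − 1.960]

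**Worked case, q = 0.20, c = 0.5.**
- f = 1: between 0.2·0.8 = 0.16; within 0.25·1.20 = 0.30; R² = 0.16/0.46 = 0.348; power = Φ(2.802·0.808 − 1.960) = Φ(0.30) = 62%.
- f = 0.5: between 0.04; within 0.25·1.05 = 0.2625; R² = 0.132; power = Φ(2.802·0.932 − 1.960) = Φ(0.65) = 74%.

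**Unstratified power (%) where the stratified analysis has 80%:**

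| Added time | CV | q = 5% | 10% | 20% | 30% |
|---|---|---|---|---|---|
| full | 0.3 | 63 | 53 | 43 | 39 |
| full | 0.5 | 73 | 68 | 62 | 59 |
| full | 0.7 | 76 | 74 | 70 | 68 |
| half | 0.3 | 75 | 71 | 65 | 62 |
| half | 0.5 | 78 | 77 | 74 | 73 |
| half | 0.7 | 79 | 78 | 77 | 76 |

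**Check by simulation with the rank tests** (116/232, full added time), Wilcoxon versus van Elteren: 49% versus 80% (CV 0.3, q = 20%), 63% versus 79% (CV 0.5, q = 20%), 76% versus 81% (CV 0.7, q = 10%). A separate simulation with 15 minutes (SD 6) per nodule, full added time and a 12% shorter time on the novel device gave 72% versus 76% at q = 5%, 65% versus 83% at 15% and 54% versus 85% at 30%. With no true difference and q = 15%, the two tests rejected in 4.5% and 4.9% of runs, so neither inflates the error rate.

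**The other endpoints, q = 5–30%.**
- Pain (same formula, VAS within-group SD 1.5): unstratified power 79–80% if multi-nodule patients score 0.5 point higher, 76–79% if 1 point, 67–77% if 2 points.
- Localization success (simulated, one-sided, patient-level rates held at 89% and 97%): chi-square 89.8–90.1%, Cochran–Mantel–Haenszel 90.0–90.2%.
- Complications (illustrative 30% versus 16%, two-sided): about 85% versus 85–86%.

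**The case against.** The strongest reply is that nothing here is an error. Unadjusted tests are valid in a randomized trial, and chance imbalance in the number of nodules is already covered by their type I error. The only power statement, "Significance level: 0.05; power: 0.8", belongs to the primary sizing, so no stated power for time is lost. The size also rests on inputs that the protocol does not give. A second nodule may add less than a full procedure time, because the CT and planning steps in 7.6 may be partly shared; with half the time added and a CV of 0.7 the loss is only 1–4 points. All of this stands. The point is therefore one of efficiency, with a conditional size.

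A reader might infer more than the documents support:

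- **That every endpoint accumulates with nodules and loses much power.** The protocol documents accumulation only for the primary, through the any-site rule. It is plausible for time and complications. A VAS score does not add up over punctures, and the pain loss is 0–4 points at SD 1.5 unless multi-nodule patients score about 2 points higher. For success and complications the gain is under 1 point.
- **That two-nodule patients have planned failure risks of 1−0.89² = 20.8% and 1−0.97² = 5.9%.** This reads the rates in 11.2 as per-site and the sites as independent. Section 11.2 says neither, and 6.1 scores success per patient.
- **That the primary should be stratified too.** If 15% had two nodules, that stratum would hold about 17 and 35 patients (0.15·116 and 0.15·232). Even on the per-site reading it would have only about 4 and 2 expected failures. Section 11.3.1 provides Fisher's exact test for small expected counts, and a Mantel–Haenszel test would give that up for almost no gain.

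**Conclusion.** The point holds for localization time, as an avoidable loss of efficiency and not as bias or an invalid test. With 5–30% of patients having two nodules and a CV of 0.3–0.7, power falls from 80% to about 39–76% if a second nodule adds a full procedure time, and to about 62–79% if it adds half. The loss is material when multi-nodule patients are fairly common and nodule times are consistent. It is minor when they are rare or times vary widely. The protocol does not let one say which applies. Because the factor is known before allocation and the protocol locks in its tests, the change is worth making in advance.

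**What to change.** In 11.3, state that localization time is compared with a van Elteren (stratified rank-sum) test, or with a linear model, using the number of nodules planned for localization (1 versus 2 or more) as stratum or covariate. Name one of the two methods in advance. Record the number from the screening CT before the envelope is opened. Do not use the number of needles used, which may depend on the device.

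The same factor may be used for VAS pain, where the gain is probably small. Leave the tests for localization success and complications as they are.

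The cost is one extra CRF field filled from an existing CT and slightly more analysis, with no extra patients or procedures. It should be written in before the analysis, because 11.8 would otherwise require ethics committee approval.

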#### 11.3.2 Case characteristics

Enrollment and completion condition: The enrolled and completed cases and the list of drop-out cases will be provided.

General information and baseline characteristics: Statistical description will be performed for the patient's demographic information and history of other diseases.

Baseline: Baseline is defined as the basic condition of the subject before clinical operation.

#### 11.3.3 Effectiveness evaluation

Successful localization rate: count conditions of successful localization, estimate the success rate.

#### 11.3.4 Safety evaluation

The statistical description will be performed for the condition of each complication. A table will be made to describe the type, severity, frequency and relationship to the investigational medical device of the AE. The incidence rate of AE will be calculated. Study discontinuation due to AEs as well as severe or serious AEs

will be specially described. The statistical description will be performed for the working condition of the system.

# 11.4 Significance Level and Power of the Trial

Significance level: 0.05; power: 0.8.

# 11.5 Expected Drop-Out Rate

The maximum drop-out rate is expected to be about 15%.

#### 11.6 Processing Method for Missing, Unused, Wrong and Unreasonable Data

Missing data of this trial will not be filled and be deemed as invalid data.

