# 6.2 Evaluation Criteria of Safety

Adverse events during the trial mainly refer to complications of localization caused by percutaneous lung puncture, mainly including:

• Pneumothorax: Air enters into the pleural cavity due to puncture and results in pneumatosis. Evaluation method: CT examination is performed before the end of localization to find whether there is any extremely

low-density air shadow in the pleural cavity near the puncture needle and whether lung tissue is compressed and shrunk to varying degrees. Pneumothorax is classified into small pneumothorax (<20%), medium pneumothorax (20%–40%) and large pneumothorax (>40%) according to the collapse degree of the lung. Pneumothorax caused by puncture generally belongs to small pneumothorax and does not require any special treatment.

- Hemorrhage: refer to pulmonary bleeding caused by a puncture. Evaluation method: CT examination is performed before the end of localization to find whether there is any diffuse or nodular shadow over the tissue around the puncture site. Bleeding exists if yes. Bleeding caused by puncture is generally shown as a flaky, cloud- or cotton-shaped effusion shadow or the effusion shadow along the needle passage. No special treatment is needed because the bleeding amount is small.
- Pleural reaction: Pleural reaction refers to a series of reactions in the process of a pleural puncture due to the diagnosis or treatment of thoracic diseases, such as cough, dizziness, chest tightness, pale complexion, sweating and even fainting. In case of pleural reaction, stop the puncture immediately, put the patient in a supine position, keep the patient warm, and observe the changes of pulse, blood pressure and consciousness. Those with mild symptoms can relieve themselves after rest. For patients with obvious sweating and low blood pressure, oxygen inhalation and 10% glucose supplement of 500 ml were given. If necessary, inject adrenaline subcutaneously to prevent shock.

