#### 7.8 Standards and Procedures for Discontinuing Trial/Treatment

- Trial discontinuation:
- (1) A huge error of the clinical verification protocol is found during the trial, and the product effectiveness can hardly be evaluated;
- (2) The sponsor or CFDA requires to terminate the trial.
- Treatment discontinuation:
- (1) Withdrawal due to the subject's reason:
  - ◆ The subject does not comply with the verification plan;
  - ◆ Other reason of the subject.
- (2) Withdrawal due to medical reasons:
  - ◆ Poor protocol compliance;
  - ◆ Serious adverse events (SAEs);
  - ◆ Serious complication.

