#### 9.2 Probability Analysis of Failure

Failure of this trial may be caused by any problem of the investigational product, that the investigator fails to strictly execute the clinical protocol, operate and measure as per the specification, and that the drop-out/rejection rate is greater than 10 %, etc. However, these factors will be controlled within the acceptable range. Therefore, this clinical trial is very unlikely to be failing.

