### 11.7 Interim Analysis and Sensitivity Analysis

This study has no interim analysis and sensitivity analysis.

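### Missing primary outcomes are dropped and sensitivity analysis is ruled out, while the protocol does not say how to score a localization that is started but not completed or a patient withdrawn before first VATS exploration

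*Protocol*

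**What the plan says.** - **Missing data (Protocol 11.6):** "Missing data of this trial will not be filled and be deemed as invalid data".
- **Checks (Protocol 11.7):** "This study has no interim analysis and sensitivity analysis". Section 11.8 requires strict adherence to the statistical plan and allows a method not named in the protocol only after ethics committee approval.
- **Drop-out:** section 11.5 says "The maximum drop-out rate is expected to be about 15" per cent. Section 11.2 builds this into enrolment ("Taking possible 15% drop-out into account"). Section 9.2 lists, among possible causes of trial failure, that the "drop-out/rejection rate is greater than 10" per cent.
- **Reasons for leaving (Protocol 7.8):** under "Withdrawal due to medical reasons" the list has poor protocol compliance, serious adverse events and serious complications. Subject-related reasons, including non-compliance, are listed separately.
- **Endpoint (Protocol 6.1):** success needs release of the device within 10 mm of the nodule edge, no dislodgement up to first VATS exploration, and no device fault or fracture. Failure at one site makes a multi-nodule patient a failure. Patients stopped or withdrawn before the outcome is complete are not mentioned.
- **Analysis set (Protocol 11.1):** the primary endpoint is analysed in the safety set, meaning device used and at least one safety record.

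**The concern.** Dropping missing outcomes is harmless only if, within each arm, patients without an outcome would have succeeded about as often as those with one. The protocol gives reason to doubt this, because some of its withdrawal reasons are harms that the localization procedure can cause. Where the endpoint definition does not decide, someone must choose between failure and missing. The trial is open-label (7.1), so that choice is made by people who know the device. The blind data review in 12.1.3 comes at data lock, after the entry has been made.

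Failures are expected to be few, so a small number of reclassified patients can matter to the success criterion in 11.2. This is not a detail left for a statistical analysis plan: 11.6 and 11.7 are positive rules, and 11.8 makes departures from them subject to approval.

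**Working it through.** **Inputs (Protocol 11.2 and 11.5).** Success 89% hookwire and 97% novel device; one-sided alpha 0.05; Fisher's exact test; 116 and 232 evaluable; 136 and 273 enrolled; 15% drop-out.

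**Step 1: the plan's own figure.** Enrolled = evaluable / (1 − 0.15). 116/0.85 = 136.5 (stated 136), 232/0.85 = 272.9 (stated 273), total 409. The inflation reproduces. Missing at that maximum: 136 − 116 = 20 hookwire and 273 − 232 = 41 novel device, 61 in all.

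**Step 2: complete cases at the design rates.** Expected failures are 0.11 × 116 ≈ 13 and 0.03 × 232 ≈ 7, or 20 in total. The 61 missing patients are about three times that number. Fisher on 13/116 versus 7/232: one-sided p = 0.003.

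**Step 3: put the missing patients back.** Denominators become 136 and 273; failures become 13 + a and 7 + b, where a of 20 and b of 41 missing patients failed.

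| Assumption about the missing | a | b | Failures, hookwire vs novel | One-sided p |
|---|---|---|---|---|
| Equal, about 10% | 2 | 4 | 15/136 vs 11/273 | 0.007 |
| Equal, about 20% | 4 | 8 | 17/136 vs 15/273 | 0.013 |
| Equal, about 40% | 8 | 16 | 21/136 vs 23/273 | 0.025 |
| Equal, about 60% | 12 | 25 | 25/136 vs 32/273 | 0.048 |
| Equal, about 70% | 14 | 29 | 27/136 vs 36/273 | 0.055 |
| 10% vs 20% | 2 | 8 | 15/136 vs 15/273 | 0.037 |
| 10% vs 22% | 2 | 9 | 15/136 vs 16/273 | 0.051 |
| All fail | 20 | 41 | 33/136 vs 48/273 | 0.073 |

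In the last row success is 75.7% versus 82.4%, still in favour of the novel device; two-sided p = 0.116. On a two-sided test the row with b = 8 already gives 0.068.

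**Step 4: false-positive rate.** Suppose both devices truly succeed in 89% and 15% are missing per arm, with a share f of the missing being failures. The observed success rate is (0.89 − 0.15(1 − f))/0.85. For f = 0.11 this is 0.89; for f = 0.20 it is 0.906; for f = 0.30 it is 0.924. With f = 0.11 in both arms the one-sided Fisher error at 116/232 is 0.035. With 0.11 for hookwire and 0.20 or 0.30 for the novel device it is 0.088 or 0.21. With f equal in both arms at 0.30 or 0.50 it is 0.031 or 0.028, so there is no inflation.

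**Step 5: scoring every unobserved outcome as failure in the primary analysis.** With 15% missing at random, success falls to 0.89 × 0.85 = 0.757 and 0.97 × 0.85 = 0.825. One-sided Fisher power at 136/273 is about 43% (about 54% with 10% missing), against about 84% for 116/232 complete cases.

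**The case against.** The other side has several good points, and most of them stand as limits on size.

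- **A reader might infer that 11.6 removes exactly the patients most likely to have failed.** No section says that a complication makes the primary outcome missing. A puncture abandoned before release can fairly be read as a non-success under 6.1. That reading is not written down, however, and it does not cover a patient whose device was released and who was withdrawn before exploration.
- **A reader might infer that a pleural reaction ends participation.** Section 6.2 says "In case of pleural reaction, stop the puncture immediately", but adds that mild symptoms settle with rest. It does not say that localization cannot then be completed, and 7.8 does not name pleural reaction.
- **A reader might infer that withdrawals are complications.** Section 7.8 also lists non-compliance and other reasons of the subject.
- **A reader might take 15% as the expected loss of outcomes after placement.** It is a maximum. Surgery follows immediately after localization (8.4), which leaves little time for loss. Patients in whom no device was used fall outside the safety set in 11.1, which is a separate matter from 11.6.
- **A reader might infer a bias in favour of the novel device.** The documents give no failure rate for missing patients in either arm. Section 1 reports many complications for hookwire and a low rate for the novel device, so the asymmetry that overturns the result is not one the protocol predicts. The direction of any bias is unknown.

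None of this removes the gap: the scoring is unstated, and the one tool that would show whether it matters is excluded.

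**Conclusion.** The point holds as a fault in the rules, not as a demonstrated bias. Sections 11.6 and 11.7 together let outcomes that may be related to the procedure drop out of an open-label primary endpoint with no check, and 6.1 does not settle how the affected patients are scored.

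At the planned maximum loss the conclusion is fairly robust to equal failure rates among the missing: significance goes only somewhere between about 60% and 70%. It is fragile to a moderate difference between arms (22% versus 10%). The calculations assume 15% missing in each arm, observed rates equal to the design rates, and failure shares among the missing that the protocol does not give. With fewer missing patients the effect shrinks.

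The mismatch between 10% in 9.2 and 15% in 11.2 and 11.5 is a separate inconsistency. It needs correcting, but it is not evidence of bias.

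**What to change.** 1. **Sections 6.1 and 11.6.** State that a patient counts as a failure in the primary analysis if localization was started but the device was not successfully released, or if the patient was withdrawn for a procedure-related complication before first VATS exploration. Other unobserved outcomes remain missing and are covered by item 2.
2. **Section 11.7.** Replace the exclusion of sensitivity analysis with a prespecified tipping-point table over the number of failures among missing patients in each arm, including the case where all missing are failures. Keep that case as a sensitivity analysis. As the primary analysis it would cut power to about 43% at 15% missing, and the sample size would have to be redone.
3. **Sections 9.2, 11.2 and 11.5.** Reconcile the 10% and 15% drop-out figures.

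**Cost.** Wording, one extra table and possibly slightly lower reported success rates. Because item 1 touches the primary endpoint, it would go to the ethics committee as a material amendment under 13.4.
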